3.4.1. Risk Assessment

The challenge agents and cantharidin used in this study are established in healthy volunteer studies and are expected to be well tolerated. The information in this section is provided in the interests of full disclosure of all potential risks.

Potential Risk of Clinical Significance	Summary of Data/Rationale for Risk	Mitigation Strategy
	Cantharidin	
Risk of lymphangitis and/or Lymphoedema	Three cases of lymphangitis and lymphoedema following high exposure to cantharidin (0.7% solution and application on multiple warts) have been described in the literature (Dilaimy, 1975, Stazzone, 1998).	Participants with a history of lymphangitis and/or lymphoedema or any participant who has undergone surgery resulting in loss of tissue associated with lymphoid drainage (e.g. certain breast surgery procedures) are excluded.
		Concentration of cantharidin is reduced in this study from 0.7% to 0.2 %.
Discomfort and/or pain at the blister site	Forearm blister induction with cantharidin has been associated with local discomfort and/or pain in previous studies.	Participants are advised to wear loose clothing at the site of blistering to minimise hyperaesthesia and discomfort that may occur.
		Pain will be assessed by asking participants to rate their pain using an 11-point scale (0 – no pain to 10 –worst pain imaginable) (Farrar, 2001).
		For immediate relief of any discomfort, paracetamol, at doses of \leq 2 grams/day will be given to the participant, unless, in the opinion of the investigator and sponsor, the medication will interfere with the study.
Risk of dyspigmentation and hypertrophic scar	After blister healing, temporary post-	Participants with history of keloids, skin allergy,

Potential Risk of Clinical Significance	Summary of Data/Rationale for Risk	Mitigation Strategy
formation	inflammatory dyspigmentation and hypertrophic scar may occur and persist for several months.	hypersensitivity, or contact dermatitis, including previous reactions to dressings to be used in this study or any chronic skin disorder (e.g. psoriasis, atopic dermatitis, vitiligo) excepting isolated lesions remote from intended site of application of cantharidin are excluded. Appropriate skin care to avoid dyspigmentation and hypertrophic scar will be implemented.
Risk of infection at the blister site	During the blister fluid harvesting, there is potential for infection at the site. To date there	To minimize the risk, appropriate clean procedures will be applied.

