6.2. Exclusion Criteria

A participant will not be eligible for inclusion in this study if any of the following criteria apply:

- 1. A positive pre-study Hepatitis B surface antigen or positive Hepatitis C antibody result within 3 months of screening
- 2. A positive test for HIV antibody.
- 3. Persistent abnormal CRP/ WCC levels at screening.
- Abnormal liver function tests at screening. For healthy participants: aspartate aminotransferase (AST), alanine aminotransferase (ALT), alkaline phosphatase and bilirubin ≥ 1.5xupper limit of normal (ULN) (isolated bilirubin >1.5xULN is acceptable if bilirubin is fractionated and direct bilirubin <35%) at screening (Refer to Appendix 1).
- 5. A positive pre-study drug/alcohol screen.
- 6. Current, or chronic history of:

- liver disease or known hepatic or biliary abnormalities (with the exception of Gilbert's syndrome or asymptomatic gallstones), anaphylaxis, and /or anaphylactoid (resembling anaphylaxis) reactions (Sampson, 2006).
- cardiac, respiratory or renal disease (childhood asthma can be included).
- Sensitivity or severe allergic responses to any of the challenge agents or cantharidin, or components thereof or a history of drug or other allergy that, in the opinion of the Investigator or GSK Medical Monitor, contraindicates their participation.
- vasovagal syncope
- surgery or significant trauma in 3 months leading to study enrolment
- relevant skin conditions (e.g. recent h/o eczema or recurrent eczema, keloid, skin allergies, psoriasis, atopic dermatitis, and vitiligo) which in the opinion of the investigator could pose safety issues or cause interference with study procedures.
- sepsis or known coagulation disorders
- peripheral oedema, lymphangitis, lymphoedema, pleural or pericardial effusion.
- respiratory conditions including but not limited to asthma, COPD, and bronchiectasis and any current respiratory infection.
- 7. Presence on either forearm of tattoos, naevi, hypertrophic scars, keloids, hyper- or hypo- pigmentation. Participants with very fair skin, very dark skin, excessive hair or any skin abnormalities that may, in the opinion of the Investigator, interfere with study assessments.

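### The risk table (3.4.1) excludes past surgery that removed lymph-draining tissue with no time limit, but the exclusion criteria (6.2) cover surgery only in the 3 months before enrolment

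*Protocol*

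**What the plan says.** **Surgery.** In the cantharidin part of the risk table (Protocol 3.4.1), the mitigation for lymphangitis and lymphoedema excludes men with a history of either condition. It then adds a separate group: "any participant who has undergone surgery resulting in loss of tissue associated with lymphoid drainage (e.g. certain breast surgery procedures) are excluded". No time window and no discretion are attached. In Protocol 6.2, criterion 6 has one bullet on surgery, "surgery or significant trauma in 3 months leading to study enrolment", and one on the conditions themselves, "peripheral oedema, lymphangitis, lymphoedema, pleural or pericardial effusion".

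**Skin.** For dyspigmentation and hypertrophic scarring, the same table lists a history of keloids or skin allergy and continues with "hypersensitivity, or contact dermatitis, including previous reactions to dressings to be used in this study or any chronic skin disorder". The only exception is the one that closes the sentence: "excepting isolated lesions remote from intended site of application of cantharidin are excluded". Criterion 6 in 6.2 instead reads "relevant skin conditions (e.g. recent h/o eczema or recurrent eczema, keloid, skin allergies, psoriasis, atopic dermatitis, and vitiligo", given as examples, and then limits the bullet to conditions "which in the opinion of the investigator could pose safety issues or cause interference with study procedures".

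**Reliance.** Section 3.4.2 says that participants gain no benefit. Section 3.4.3 concludes that the measures taken against the cantharidin, LPS and GM-CSF risks are enough to justify taking part.

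**The concern.** The risk table tells an ethics committee that a defined group will not be exposed. The criteria against which volunteers are screened do not say the same. Section 9 requires screening evaluations to be reviewed to confirm that all eligibility criteria are met, so a screener working through 6.2 has no prompt to ask about surgery older than 3 months that removed lymph-draining tissue.

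At stake is whether a stated safety mitigation can be enforced. The sponsor's own table treats this surgery as a risk factor additional to lymphangitis and lymphoedema. Under section 7.2 every participant has 4 blisters in each of 2 sessions (4 × 2 = 8), all on the forearms. Where volunteers receive no benefit, a mitigation used to justify the risk should be one that the entry criteria deliver.

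**Working it through.** No arithmetic bears on this point, and the plan gives no figure to reproduce. The check sets the risk table against the eligibility criteria (6.1 and 6.2) and asks, for each history, which text bars entry.

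**1. Lymph-draining surgery more than 3 months ago, no oedema or lymphatic disease**
- 3.4.1: barred, whatever the date.
- 6.2 criterion 6, surgery bullet: not met, because the surgery is outside the 3-month window.
- 6.2 criterion 6, oedema and lymphatic bullet: not met. It lists the conditions, not the surgery.
- 6.2, remaining criteria: none names it.
- 6.1, inclusion criterion 2 (overall health on medical evaluation): a general judgement that could lead to exclusion but does not name it.
- Result: excluded in one section, no listed exclusion in the other.

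**2. The same surgery within 3 months**
- Both sections bar entry. No conflict.

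**3. History of lymphangitis or lymphoedema**
- Both sections list these conditions. Not part of the gap.

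**4. History of contact dermatitis or of a reaction to a study dressing**
- 3.4.1: barred, unless covered by the exception for isolated lesions away from the application site.
- 6.2 criterion 6, skin bullet: names neither, but the list is open and skin allergies are one of its examples. It applies only if the investigator sees a safety or procedural problem.
- 6.2 criterion 6, allergy bullet: the challenge agents, cantharidin and their components are named. Any other allergy counts only if the investigator or medical monitor judges that it rules out participation.
- 6.2 criterion 7: concerns forearm skin findings, and other skin abnormalities at the investigator's discretion. It does not address a past history as such.
- Result: a flat exclusion in one section, a matter of judgement in the other.

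**5. Is 6.2 meant to carry the risk-table exclusions?** The pattern suggests so. The respiratory row of the table refers the reader to the exclusion criteria. The table's other history-based exclusions also appear in 6.2: vasovagal syncope, earlier experimental LPS exposure, and cardiac, respiratory, renal and liver disease. The surgery exclusion did not carry over, and the skin exclusion carried over only in weakened form. That looks like a drafting omission rather than a decision, although the documents do not say.

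**The case against.** The strongest reply is that 3.4.1 is itself protocol text. Appendix 3 requires the study to be run in accordance with the protocol, and sections 6 and 9 rule out waivers. Enrolling a man with this surgical history would contradict 3.4.1, so it is wrong to say that no written rule exists. That stands. A reader might infer that these men may freely be blistered, or that written protection is nil. The documents do not support this: the rule exists, but it is missing from the list used to decide entry.

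The skin half is also weaker than the surgery half. The 6.2 skin bullet gives examples rather than a closed list, skin allergies may capture some of these men, and the allergy bullet, criterion 7 and the overall-health criterion give further room to exclude. That stands too, and it makes the skin mismatch secondary.

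Other lymphatic safeguards are intact. Lymphangitis and lymphoedema are excluded in 6.2, and the cantharidin is diluted from 0.7% to 0.2%. The three lymphatic cases cited in the table followed high exposure at 0.7% on multiple warts. The table's only surgical example is breast surgery, while the trial enrols healthy men aged 18 to 45. All of this bears on how often the gap would matter, not on whether the two sections agree.

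Finally, a reader might infer that a dressing reaction would distort the study's results. Nothing in the documents says so. The primary endpoints are in blood and urine, blister measures are secondary, and pain and healing time are exploratory. Blisters are induced in both sessions of the same participant, so a reaction need not be confined to the challenge session.

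**Conclusion.** The point holds for surgery: 3.4.1 and 6.2 give different answers for a man with older lymph-draining surgery and no resulting condition, and 6.2 as written does not deliver the mitigation. It holds as a lesser point for contact dermatitis and dressing reactions, where a flat exclusion has become a discretionary one.

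The size is small. Enrolment is capped at 40, and it would be tempting to say that the mitigation is missing for all of them. The gap concerns only men with one of these histories. That they are few is an assumption based on the population, since no frequency is given. There is no effect on sample size or planned analyses.

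It is nonetheless more than an editorial slip, because 3.4.3 relies on the mitigations. The conclusion assumes that eligibility is checked against 6.1 and 6.2 rather than against the risk table, which is how section 9 reads.

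**What to change.** Reconcile 3.4.1 with criterion 6 of 6.2 so that the mitigation and the enforceable criteria match. There are two routes, and which rule applies is for the sponsor to decide:

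- Carry the 3.4.1 exclusions into 6.2 as their own bullets: lymph-draining surgery without the 3-month limit, and contact dermatitis or past reaction to the study dressings. State whether and how the exception for isolated lesions away from the application site applies.
- Or amend 3.4.1 to describe what 6.2 actually excludes, and restate the residual risk on which 3.4.3 rests.

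The first route costs one or two bullets in an amendment and matching screening questions. It may also lose some volunteers. Their number is unknown, and a flat bar on any history of contact dermatitis could account for more of them than the surgery bullet. The second route costs a revision of the risk text only.

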2. SCHEDULE OF ACTIVITIES (SOA)

Any changes in the timing or addition of time points for any planned study assessments must be documented and approved by the relevant study team member and then archived in the sponsor and site study files, but will not constitute a protocol amendment. The IRB/IEC will be informed of any safety issues that require alteration of the safety monitoring scheme or amendment of the ICF.

2016N309726_01

CONFIDENTIAL

207654

PROCEDURE	Screening	SI	ESSION	1	Interim inspectio n		SESS	ION 2		1st follow-up	2nd follow-up		
Day:	Within 30 days of Day 1	Day 1	Day 2	Day 3	Minimum 2 wks (max 4 weeks) after end of session 1	Day -1	Day 1	Day 2	Day 3	Minimum 2 wks (max. 4 weeks) after end of session 2	Approx. 5wks after end of session 2		
Attend Unit	Х	Х	Х	Х	Х	X3	Х3	Х	Х	Х	Х	1.	Brief physical exam only
Informed Consent	Х											2.	Within an hour before
Inclusion/Exclusion checklist	Х					Х							cantharidin application
Medical /medication history	Х											3.	Overnight stay in the unit
Demographics	Х											4.	Additional clinical lab
Body weight	Х					Х							assessments may be
Drug/alcohol test	Х	Х				Х						_	performed, if necessary
Physical Exam	Х	X1				Х	X ¹			X1		5. 6.	Before blister fluid sampling After the last blister fluid
Vital Signs and temperature	Х	X2				Х	X8	Х		Х	Х	0.	sampling at each session
ECG	Х					Х	Х					7.	Multiple blood draws at the
Telemetry							Х						following time points: Pre
Visual forearm check (including blister healing and cosmetic assessment)	Х	X ²			Х	Х	X ²			Х	Х		challenge, , 5 mins (i.e. Pre-blister induction), 10 min, 25 min, 40
Cantharidin application (Session 2 only: 20 minutes post end of LPS or GM-CSF challenge)		Х					Х						min, 1hr:10mins, 1hr:40mins, 2hr:40mins, 5hr:40mins with respect to start of blister induction
AE assessment/Con Meds		«-									»	8.	Every half hour for the first 4
SAE	«-										»	1	hours after challenge, hourly
Clinical Chemistry, Haematology, and Urinalysis	Х	Х	Х	Х		X	Х	Х	Х				until 8 hours and then 8 hourly until discharge. Frequency can be increased if symptomatic
Mediators blood sample		X2	X5	X5			X7	X5	X5			9.	For flow cytometry and
Flow cytometry blood sample		X2	X5	X5			Х9	X5	X5				transcriptomic blood samples:
For LPS only: Ex vivo							X ¹⁰						Multiple blood draws at the

2016N309726_01

CONFIDENTIAL

207654

PROCEDURE	Screening	SE	SSION	1	Interim inspectio n		SESS	ION 2		1st follow-up	2nd follow-up		

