Risk of Respiratory Symptoms	Sequestration of granulocytes in the pulmonary circulation has been documented following LEUKINE infusion12 and dyspnoea has been reported occasionally in patients treated with LEUKINE. Special attention should be given to respiratory symptoms during or immediately following LEUKINE infusion, especially in patients with pre-existing lung disease. In patients displaying dyspnoea during LEUKINE administration, the rate of infusion should be reduced by half. If respiratory symptoms worsen despite infusion rate reduction, the infusion should be discontinued. Subsequent IV infusions may be administered following the standard dose schedule with careful monitoring. LEUKINE should be administered with caution in patients with hypoxia.	Patients with known respiratory disease will be excluded from the study (as described in the Exclusion criteria), as well as patients with current or recent (<30 days) infection.
Risk of cardiovascular Symptoms	Occasional transient supraventricular arrhythmia has been reported in uncontrolled studies during LEUKINE administration, particularly in patients with a previous history of cardiac arrhythmia. However, these arrhythmias have been reversible after discontinuation of LEUKINE.	Patients with pre-existing cardiac disease will not be eligible to participate. In addition, we will use telemetry for a minimum of 6 hours following dosing, or until normal for 4 hours (whichever is longer).

2016N309726_01

CONFIDENTIAL

Potential Risk of Clinical Significance	Summary of Data/Rationale for Risk	Mitigation Strategy
	LEUKINE should be used with caution in patients with pre-existing cardiac disease.	

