6.1. Inclusion Criteria

Participants are eligible to be included in the study only if all of the following criteria apply:

Age

1. Participant must be 18 to 45 years of age inclusive, at the time of signing the informed consent.

Type of Participant and Disease Characteristics

2. Participants who are overtly healthy as determined by medical evaluation including: medical history, physical examination, laboratory tests, and ECG.

Weight

3. Body mass index (BMI) within the range $19.0-30.0 \text{ kg/m}^2$ (inclusive).

Sex

4. Male

All participants must agree to use contraception as detailed in Appendix 5 of this protocol during session 2 and refrain from donating sperm from session 2 to end of study (follow-up 2 visit).

Informed Consent

Capable of giving signed informed consent as described in Appendix 3 which includes compliance with the requirements and restrictions listed in the informed consent form (ICF) and in this protocol.

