12.2. Appendix 2: Clinical Laboratory Tests

- The tests detailed in 2 will be performed by the local laboratory.
- Protocol-specific requirements for inclusion or exclusion of participants are detailed in Section 6 of the protocol.
- Additional tests may be performed at any time during the study as determined necessary by the investigator or required by local regulations.

 Table 2
 Protocol-Required Safety Laboratory Assessments

Laboratory Assessments	Parameters					
Hematology	Platelet Count RBC Count Hemoglobin Hematocrit		RBC Indices: MCV MCH %Reticulocytes		WBC count with Differential:	
					Neutrophils	
					Lymphocytes Monocytes	
	PT and APTT (at				Eosinophils	
	screening only)				Basophils	
Clinical	BUN	Pota	ssium	Aspartate		Total and direct
Chemistry ¹				Aminotransfe (AST)	rase	bilirubin
	Creatinine	Sodium		Alanine Aminotransferase (ALT)		Total Protein
	Glucose (fasted	Calcium		Alkaline		CRP
	glucose at			phosphatase		
	screening only)					
	Albumin	Urea	a Corrected calcium		lcium	
Routine Urinalysis	 Urine cotinine Specific gravity pH, glucose, protein, blood, ketones by dipstick Microscopic examination (at investigator discretion if blood or protein urine dipstix is abnormal.) 					
Other tests	 HIV Hepatitis B (HBsAg and HBcAb) Hepatitis C (Hep C antibody) Alcohol and drug screen (to include at minimum: amphetamines, barbiturates, cocaine, opiates, cannabinoids and benzodiazepines) 					

NOTES :

1. Local urine testing will be standard for the protocol unless serum testing is required by local regulation or IRB/IEC.

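### Protocol Section 3.4.1 relies on a 30-day infection exclusion that the eligibility criteria in Section 6.2 do not contain

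*Protocol*

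**What the plan says.** The risk table in Protocol Section 3.4.1 has a GM-CSF row on respiratory symptoms. Its mitigation column names two exclusions. The first is "Patients with known respiratory disease will be excluded from the study (as described in the Exclusion criteria"). The second is "as well as patients with current or recent (<30 days) infection". The row does not say from which date the 30 days are counted, or whether infection means respiratory infection only.

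Appendix 2 (Section 12.2) points to where eligibility is set: "Protocol-specific requirements for inclusion or exclusion of participants are detailed in Section 6 of the protocol". The opening of Section 6 rules out waivers of the enrolment criteria.

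The items in Section 6.2 that bear on infection are:

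- the hepatitis B and C tests (item 1) and the HIV test (item 2);
- "Persistent abnormal CRP/ WCC levels at screening" (item 3);
- within item 6, sepsis, and "respiratory conditions including but not limited to asthma, COPD, and bronchiectasis and any current respiratory infection".

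Inclusion criterion 2 in Section 6.1 adds a general-health requirement: "Participants who are overtly healthy as determined by medical evaluation including: medical history, physical examination, laboratory tests, and ECG".

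**The concern.** Section 3.4.2 states that participants gain nothing from taking part, and Section 3.4.3 concludes that the listed measures are enough to justify their participation. That conclusion depends on the measures being applied. A site that follows Section 6 as written could give GM-CSF to someone whom 3.4.1 says is excluded. What is at stake is a stated safety rule in healthy volunteers, not the precision or bias of an estimate.

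**Working it through.** No calculation in the plan is involved. The check sets the promised exclusion against each control that might deliver it, for three kinds of participant.

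| Control | Infection resolved within 30 days | Mild current non-respiratory infection | Current respiratory infection |
|---|---|---|---|
| 6.2 items 1 and 2 (hepatitis, HIV tests) | Not caught, unless one of these viruses | Not caught, unless one of these viruses | Not caught |
| 6.2 item 3 (CRP, white cells) | Not caught once values are normal | Caught only if values stay abnormal at screening | May be caught |
| 6.2 item 6, sepsis | Not caught | Not caught | Not caught |
| 6.2 item 6, respiratory bullet | Not caught (current infection only) | Not caught | Caught |
| 6.1 criterion 2 (general health) | Does not address a past infection | May be caught, by judgement | Likely caught |

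**Look-back count.** Section 6.2 has 10 numbered and 3 unnumbered criteria, so 10 + 3 = 13. The number with a look-back for infection is 0. The three-month window in item 1 applies to the hepatitis test result. The lead-in to item 6 covers a current condition or a chronic history, and a single resolved infection is neither.

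**Look-backs appear where the authors wanted them.** Item 6 itself has "surgery or significant trauma in 3 months leading to study enrolment". Elsewhere 6.2 uses 6 months for smoking and 90 days for an investigational product. The respiratory, cardiac, renal, hepatic, vasovagal and previous-LPS exclusions promised in 3.4.1 all reach 6.2. The 30-day infection clause does not.

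**Other parts of the protocol.**

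- Schedule of Activities: "Medical /medication history" is marked at screening only. The inclusion/exclusion checklist is repeated at Session 2 Day -1, but it can only check criteria that exist.
- Session 2 Day -1 also has an examination, temperature and laboratory tests, which under Appendix 2 include CRP and white cells. These describe the present state and are tied to no infection criterion.
- Section 9.1.1: adverse events are collected from Session 1, so an infection would be recorded, but this triggers no eligibility rule.
- Section 6.2 item 8 and Section 7.5: the drug restrictions help only if the infection was treated, and 7.5 allows exceptions.
- Section 8.1: withdrawal by the investigator is discretionary.

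**Reach.** Protocol Section 10.1 gives 28 + 8 + 4 = 40 participants at most; at 1:1 about 40 / 2 = 20 would receive GM-CSF. SAP Section 3.1 records dose escalation as complete, so a change now reaches mainly Part II: up to 8 participants, 8 / 2 = 4 on GM-CSF, and none if Part II does not open.

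**The case against.** The best defence is that the row concerns respiratory symptoms, so infection there may mean respiratory infection. Item 6 already bars a current one, so half of the promise is kept. This reading is fair, and the text does not settle it. It narrows the gap without closing it: a respiratory infection that resolved two weeks before challenge falls within 3.4.1 and still meets no exclusion in 6.2.

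It can also be said that the cross-reference in Appendix 2 does not void exclusions stated elsewhere, and that a careful investigator would honour 3.4.1. That is possible, but Section 6 is the list a site works from, and nothing there prompts the question.

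The exposure is limited, and this stands in full. The selected GM-CSF dose of 60 µg/m² is about a quarter of the recommended daily dose of 250 µg/m² (60 / 250 = 0.24). Participants stay overnight on Day -1 and Day 1. Vital signs, including respiratory rate and SpO2, are taken half-hourly for 4 hours after challenge. These measures detect a reaction and limit its consequences; they do not exclude anyone.

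Three stronger readings are tempting and unsupported:

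- A reader might infer that any mild infection passes every criterion. For a mild current non-respiratory infection the accurate statement is that it can pass, because the general-health criterion and item 3 may stop it.
- A reader might infer that volunteers were told of an exclusion that is not applied. The participant leaflet and consent form are not available here, so this cannot be said.
- A reader might try to express the gap in days before challenge. Section 3.4.1 gives no anchor date, so such a figure would describe a hypothetical rule.

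**Conclusion.** The mismatch is real. One clause of the GM-CSF mitigation in 3.4.1 has no counterpart in 6.2, and no redaction or amendment entry explains its absence. For an infection that resolved within 30 days and left CRP and white cells normal, the gap is certain under either reading of infection, apart from the viruses tested for in items 1 and 2. For a mild current non-respiratory infection it is possible, and it matters only if 3.4.1 means infection at any site. Overt current infection is largely covered.

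The documents give no figure for the added risk from a resolved or mild infection, and none is asserted. No effect on the endpoints is claimed. The change should be made because it restores the sponsor's own rule, or corrects the statement of it, at little cost. It would reach at most a handful of people.

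**What to change.** Add to Section 6.2 a criterion excluding current infection, or infection within 30 days before challenge. Challenge is a proposed anchor, chosen because the risk arises then. If only respiratory infection is meant, say so in the same words in 3.4.1 and 6.2. State whether trivial localised infections count, so that they do not cause needless deferrals.

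Check the criterion with one direct question at the existing Session 2 Day -1 inclusion/exclusion checklist, and defer or replace the participant if the answer is positive. Section 3.4.1 promises the exclusion only for GM-CSF. Section 6.2 is common to both agents, though, and a single rule keeps eligibility independent of the randomised allocation.

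If the sponsor does not intend a look-back, correct 3.4.1 to match 6.2 instead.

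The cost is a protocol amendment with IEC/IRB approval (Section 12.3) and an occasional deferral. A deferral of up to 30 days adds up to 30 / 7 = 4.3 weeks to participation of about 13 weeks. It also lengthens the interval from the Session 1 blister and urine baselines. The documents give no infection rate. If 5% to 20% of participants had an infection in the 30 days before challenge (an assumption), 8 × 0.05 = 0.4 to 8 × 0.20 = 1.6 of the 8 Part II participants would be affected. Deferral is preferable to replacement, because the allowance of up to 4 replacements in Section 10.1 covers Parts I and II together and the documents do not show how many Part I used.
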